NOTE: Although the eligible population of the HIV clinic at AKTH is 40% male, we anticipate that females will be more likely to enroll in this study, given our previous experience. Therefore, study staff will specifically target males for enrollment in order to achieve a gender balance in our study enrollment. Strategies that will be utilized by staff include use of male counselors in the clinic, utilization of male peer counselors for targeted recruitment, and extension of clinic hours to accommodate male participants who may not be able to attend otherwise due to work engagements. These strategies have all been utilized successfully by our team in previous studies and HIV scale-up efforts within Nigeria and Mozambique.¹¹⁸⁻¹²⁰ In addition, given preliminary Aim 1 data, with the mean duration of ART among enrolled aim 1 participants being > 8 years, strategies will be utilized by staff to prioritize the identification of persons more recently (within the past 6-24 months) in order to enroll a large cohort of HIV-positive adults with a more balanced duration of time on ART. Lastly, also given preliminary Aim 1 data review coupled with DSMB feedback (January 23, 2019), it was seen that ~ 75% of enrolled aim 1 participants (n = 380) had a self-reported ethnicity of Hausa/Fulani; with only \sim 4-5% self-reporting their ethnicity as Yoruba. Based on published literature to date^{39,40}, carriage of the *APOL1* high risk (HR) genotype has been shown to be highest among persons of Yoruba descent and other ethnic groups (i.e. lgbo) and more prevalent in the southern part of Nigeria. To address this in order to increase enrolment of persons of Yoruba descent, we will plan to open a second study site; namely the Infectious Disease Hospital that is also in Kano, as the demographics of the population this hospital serves is guite different when compared to AKTH in that they service significantly higher proportions of persons of Yoruba and other ethnicities from southern Nigeria; where proportions of the population possessing the APOL1 HR genotype are highest^{39,4039-40}.

Inclusion and exclusion criteria to be used for participant enrollment into Study Aim 2 are shown below.

Inclusion criteria:

- Participated in Study Aim 1: prevalence of *APOL1* high risk status and clinical correlates

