CA) targeting the 3 chromosome 22 APOL1 variants (rs73885319 [G1], rs60910145 [G1], and rs 71785313 [G2]) associated with CKD and HIV-associated kidney disease. The APOL1 risk alleles are defined by the G1 haplotypes (rs73885319-G/rs60910145-G and rs73885319-G/rs60910145-T) and by the G2 haplotype (rs71785313-deletion). We will infer the APOL1 genotype from the number of risk alleles: individuals exhibiting two risk alleles (G1/G1, G1/G2, or G2/G2) will be assigned to the "high-risk (HR)" group, while individuals carrying no or one risk allele (G0/G0, G0/G1, and G0/G2) will be attributed to the "low-risk (LR)" group. We will also examine the risk allele groups in a categorical manner (0 vs. 1 vs. 2 alleles and 0 vs. 1 risk alleles) to determine whether presence of a single risk allele poses increased risk. We will then determine the overall prevalence of APOL1 risk alleles, including odds ratios for baseline CKD and albuminuria, and the standard error for beta comparing levels of microalbuminuria and eGFR stratified by genotype (including testing for association between the APOL1 genotype and longitudinal eGFR slope using linear regressions). In addition, we will perform crude and adjusted linear regression analyses (modified Poisson regression) to test for associations with mean uACR, eGFR, and CKD, adjusting for sex, blood pressure, and age. Based on previous genetic association work in HIVAN, we will test both additive and recessive genetic models to capture all potential risk alleles associated with microalbuminuria and CKD. Because of the strong associations reported for APOL1 with HIVAN (OR=29, U.S. and OR 89, South African, recessive model), our cohort exhibits substantial power to detect the effects of APOL1 in the recessive model. For APOL1, we anticipate that 12% of controls and 36% of cases will carry the APOL1 HR genotype; this is a strong epidemiological association, but modest on the scale of known effects of APOL1 risk alleles on kidney disease.

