Nigeria standard of care: The Nigeria HIV/AIDS adult treatment guidelines recommend a baseline assessment of all HIV-positive patients to include a complete history and physical examination, staging of disease with clinical and immunological classification of the patient, and review of laboratory results. In addition, an evaluation of nutritional and psychosocial status, assessment of readiness for therapy, and development of patientspecific adherence strategy is recommended for all patients. All HIV-positive patients, regardless of CD4+ cell count (commonly referred to as the "Test-and-Start" or "Treat All" strategy) are started on ART. First line regimens include: tenofovir (TDF) + lamivudine (3TC) + efavirenz (EFV); TDF + 3TC + nevirapine (NVP); zidovudine (AZT) +3TC (or emtricitabine [FTC]) + EFV and AZT +3TC (or FTC) + NVP. A boosted protease inhibitor plus 2 nucleoside reverse transcriptase inhibitors (NRTIs) are recommended for second-line ART, and available protease inhibitors include ritonavirboosted lopinavir and atazanavir. The government of Nigeria will be transitioning to TLD (tenofovir, lamivudine, plus the integrase strand inhibitor dolutegravir) during 2018-2019. As a result, all HIV positive persons (> 10 years of age and weighing > 30 kilograms) will be switched to TLD during this transition period in accordance with national guidelines/WHO recommendations. In patients with renal insufficiency, i.e. a documented increase in serum creatinine, the guidelines recommend ART regimen dosage modifications if the calculated creatinine clearance (CrCl) is reduced at baseline (i.e. not initiating tenofovir in adult patients having a calculated eGFR of < 50 ml/min/1.73m² or if at any time during follow-up their CrCl decreases significantly (i.e. confirmed to $< 50 \text{ ml/min/1.73m}^2$ from their baseline values). Modifications include switching patients from tenofovir to abacavir as well as investigating potential causes of their worsening renal function (i.e. looking for pre-renal causes such as dehydration, post-renal causes (prostatic obstruction, nephrolithiasis, and/or intra-renal causes such as initiation of new potentially nephrotoxic medications (such as traditional medicines, etc.). Of note, patients switched to dolutegravir (from efavirenz or nevirapine) as part of the soon to commence TLD rollout may also experience a sustained increase in their serum creatinine coupled with a corresponding decrease in their calculated eGFR. In brief, for a period of up to 48 weeks following dolutegravir (DTG) initiation, it is anticipated that study participants may experience a modest (0.2 mg/dL) increase in serum creatinine¹²⁷⁻¹²⁹ that will not lead to significant changes in uACR values but will be lead to aim 2 study participants having a "new baseline eGFR" that is unrelated to study medication and based on the literature using iohexol ¹³⁰ will not represent a true change in eGFR; but nonetheless will still need to be accounted for in the analysis plan. NOTE: Given the known limitations of CysC-based equations for HIV-positive individuals, from an analysis standpoint, the team will utilize/rely on significant changes in serum creatinine (sCr) safety monitoring/reporting among DTG-treated study participants. Patients with reductions in CrCl should undergo an evaluation for potential causes of decreased renal function and have serum creatinine monitored more frequently until

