	creatinine (sCr) (up to 0.2 mg/dL) that	(using CKD-EPI-Cr-CyC equation);
	may persist for up to 48 weeks (or	immediately HOLD study medication; look
	possibly longer) so to account for these	for other possible etiologies/contributing
	potential modest changes in renal	factors; and monitor closely; repeating eGFR
	function, all safety events involving kidney	within 1 week; involve the SOC/SSC; as
	function deemed "possibly" or "definitely	study medication may need to be discontinued
	related" to study medication among DTG-	and AE report done
	treated study participants will be	
	evaluated and graded using serum	
	creatinine (sCr) measurements.	
Step 2 to 3	Same as above for Step 1	Same as above for Step 1
(10 mg/d		
20 mg/u)		

Step 23to 4 (20 mg/d ↑ to 40 mg/d)	Same as above for Step 1	Same as above for Step 1

Risks of prescribed combination antiretroviral therapy (ART) (specifically tenofovir (TDF):

All eligible/enrolled aim 2 study participants will be receiving ART for 6+ months, and we anticipate that a significant proportion (i.e. > 80%) of them will be receiving tenofovir (TDF)-based regimens. We mention this because of the potential adverse events that have been attributed to the nucleotide reverse transcriptase inhibitor TDF, namely kidney toxicity which may manifest as a reduction in eGFR. These potential TDF-associated kidney manifestations that include reduced eGFR, Fanconi's syndrome, etc. are due to tubular (rather than glomerular) insults; and they often present within the first 1-2 years following TDF initiation and based on our preliminary analysis of enrolled aim 1 study participants (January 2019), the majority of aim 1 study participants (from which we will be screening/enrolling for aim 2) have been receiving ART for considerably longer periods of time (i.e. mean duration of ART > 8 years).

Management of Worsening Renal Function Among Study Participants receiving tenofovir (TDF)-based ART regimens:

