8.0 Statistical Considerations

[figure not shown]
Specific Aim 1

Sample size justification: A screening sample size of 2,600 participants will yield sufficient sample size for randomization in Specific Aim 2 detailed below. With 2,600 persons screened for Aim 1, the prevalence of *APOL1* renal risk variants may be estimated with precision (half-length of the 95% confidence interval) equal to 0.02 or better. Assuming a microalbuminuria prevalence of 17.5% based on recent data obtained from HIV-positive adults (n ~ 460) screened at AKTH,¹¹⁰ where this study will take place, we will have 90% power to detect a relative risk of microalbuminuria of 1.37 or higher in participants with renal risk variants compared to participants without, and we anticipate that 1 in 4 participants will have renal risk variants. We estimate, based on our experience with our studies at this site, that enrollment for Aim 1 will take 12 months. In addition to analyzing *APOL1* risk as a binary high/low risk status, we will also examine relative risk of microalbuminuria with *APOL1* risk categorized based on the presence of 0, 1, or 2 alleles, as this will lead to an increased understanding of the risk associated with the presence of a single risk allele.

Statistical analysis plan: We will estimate the prevalence and associated 95% confidence interval of *APOL1* renal risk variants. We will test whether the presence of these variants is associated with log₁₀uACR or eGFR using Wilcoxon rank sum test. Multivariable linear regression for each of log₁₀uACR or eGFR will be used to adjust for potential confounders, including: sex, age, CD4+ cell count, viral load, and the presence/absence of specific comorbid medical conditions (hypertension, cardiovascular disease, diabetes mellitus, etc.). For linear regression, appropriate transformations of dependent variables will be used to satisfy modelling assumptions. To relax linearity assumptions, covariates will be modelled using restricted cubic splines.¹³⁵ Modified

Poisson regression adjusted for similar variables, will be used to assess associations with prevalent CKD, microalbuminuria, and reduced eGFR (< 60 mL/min/1.73m²), and 95% confidence intervals.

Specific Aim 2 Sample size justification: We will

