Statistical analysis plan: Our first approach will be to perform an intent-to-treat analysis, but we will also perform an on-treatment analysis to compare these data and present all available findings. *Primary analysis*: We will test the hypotheses that regression and progression rates are different across arms using multivariable Cox regression models with the intervention variable (randomization to RAAS [yes/no]) as the primary predictor variable, adjusting for baseline (pre-randomization) covariates including baseline uACR, *APOL1* renal risk variants, CD4+ cell count, blood pressure

ART regimen (DTG vs. other), and the presence/absence of comorbid medical conditions (hypertension, cardiovascular disease). To relax linearity assumptions, baseline uACR will be included in models using restricted cubic splines.¹³⁸ Primary analyses will be intention to treat, although we also plan to perform "per protocol" analysis. We will also test the impact of study arm on uACR using a linear mixed effects model to account for within patient correlation with the outcome of 3-monthly uACR values (with primary endpoints obtained by evaluating the uACR and other key renal outcomes at 18 and 30 months given that all enrolled study participants will not be placed or sustained on their maximum tolerated lisinopril dose or matched placebo until 6 months after study enrollment). The model will also adjust for the baseline covariates given above. For this analysis, we anticipate log-transforming uACR to meet modelling assumptions, although other transformations will be considered if needed.

Secondary analyses: Analyses for secondary endpoints will be similar to that described above. Time-to-event outcomes (doubling of serum creatinine from baseline, all-cause mortality, 40% decline in eGFR, and tenofovir toxicity) will be assessed using multivariable Cox regression models. Continuous outcomes (eGFR, quality of life metrics, and blood pressure) will be analyzed using mixed effects models after proper transformation of the outcome variable, if necessary. Baseline covariates listed above will be included in all secondary analyses.

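### The Aim 1 eGFR and CKD models name no ART regimen, time on ART, ethnicity, site or enrolment period, although recruitment was widened towards higher APOL1 carriage during the dolutegravir rollout

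*Combined protocol and SAP*

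**What the plan says.** **Aim 1 models.** Section 8.0, Specific Aim 1, first tests eGFR and log uACR against genotype with an unadjusted Wilcoxon test. It then fits linear models for potential confounders, including "sex, age, CD4+ cell count, viral load, and the presence/absence of specific comorbid medical conditions". The binary outcomes follow: "Poisson regression adjusted for similar variables, will be used to assess associations with prevalent CKD, microalbuminuria, and reduced eGFR". Section 5.0 (Genetics specimen collection and analysis) gives a different, shorter list: "to test for associations with mean uACR, eGFR, and CKD, adjusting for sex, blood pressure, and age". No list names ART regimen, time on ART, ethnicity, site or enrolment period.

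**Recruitment.** Section 3.0 (Recruitment strategies) reports 380 Aim 1 participants at the January 2019 review, about 75% of them Hausa/Fulani, with mean ART duration above 8 years. Two changes follow. Staff will "prioritize the identification of persons more recently (within the past 6-24 months". A second Kano site is also planned, because it serves more Yoruba and other southern groups, in whom high-risk carriage is said to be highest.

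**Dolutegravir.** Section 5.0 (Nigeria standard of care) places the national switch to a DTG regimen in 2018-2019 and expects creatinine to rise by about 0.2 mg/dL. The titration table in Section 6.0 says up to 0.2. Section 5.0 says the resulting new baseline eGFR in Aim 2 participants "will not represent a true change in eGFR; but nonetheless will still need to be accounted for in the analysis plan", and that uACR should not change significantly. The Aim 2 covariates in Section 8.0 include "ART regimen (DTG vs. other), and the presence/absence of comorbid medical conditions".

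**Tenofovir.** Section 6.0 says of tenofovir kidney effects that "they often present within the first 1-2 years following TDF initiation". It sets against this the mean ART duration above 8 years seen in January 2019.

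**The concern.** Aim 1 is observational, so its genotype comparison has only the covariates to protect it. In Aim 2, randomisation already guards the arm comparison against baseline regimen, yet Aim 2 is where DTG is named.

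The route to bias is short. If later enrolees carry the high-risk genotype more often and are also more often on DTG, then DTG use is associated with genotype in the pooled sample. DTG lowers calculated eGFR, so the high-risk group shows lower eGFR and more people below 60 mL/min/1.73 m² even if APOL1 has no effect. That is the direction of the Section 1.1 hypothesis. At stake are eGFR, reduced eGFR and the eGFR component of CKD. Microalbuminuria, on which Aim 1 is powered, is not at stake by this route.

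**Working it through.** **1. The plan's own Aim 1 figures.** Inputs from Section 8.0: N = 2,600, one in four high-risk (650 vs 1,950), microalbuminuria 17.5%, relative risk 1.37, power 90%. Alpha is not stated for Aim 1; two-sided 5% is assumed.
- Low-risk prevalence = 0.175 / (0.75 + 0.25 × 1.37) = 0.160; high-risk = 0.160 × 1.37 = 0.219. Power is 91.9%, close to the stated 90%.
- Prevalence half-width = 1.96 × √(p(1−p)/2,600) = 0.0166 at p = 0.25 and 0.0192 at p = 0.5, both within the stated 0.02.

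These figures stand. The plan gives none for eGFR.

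**2. Precision of the eGFR comparison.** Assume an eGFR SD of 20 mL/min.
- SE = 20 × √(1/650 + 1/1,950) = 0.91; 95% half-width = 1.96 × 0.91 ≈ 1.8 mL/min.

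**3. Bias formula.** With no APOL1 effect, the false difference = A × gap. A is the fall in calculated eGFR on DTG. The gap is the DTG share in high-risk minus that in low-risk participants. The documents give neither, so A = 5, 10 and 15 mL/min are assumed. False-positive rate at nominal 5%:

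| Gap | A = 5 | A = 10 | A = 15 |
|---|---|---|---|
| 10 points | 0.5 mL/min, 9% | 1.0, 20% | 1.5, 38% |
| 20 points | 1.0 mL/min, 20% | 2.0, 60% | 3.0, 91% |

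**4. How large can the gap be?** The only split documented is 380 enrolled by January 2019, leaving 2,600 − 380 = 2,220. Keep 650/1,950 by genotype and let DTG go from 0% to 100%.
- No high-risk carriers among the first 380: high-risk DTG share = 100%; low-risk = (1,950 − 380)/1,950 = 80.5%; gap = 19.5 points. This is the ceiling.
- 12% carriage among the first 380 (45.6 people): high-risk share = 604.4/650 = 93.0%; low-risk = (1,950 − 334.4)/1,950 = 82.9%; gap = 10.1 points.

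**5. Two-wave model.** Assumed high-risk share by wave: 5% then 30%, 10% then 25%, or 12% then 20%. Assumed DTG share: 0% then 50%, or 10% then 90%.
- Worked case (5% then 30%; DTG 10% then 90%; A = 10; split 380/2,220): high-risk n = 19 + 666 = 685, low-risk n = 361 + 1,554 = 1,915. DTG shares are 601.3/685 = 87.8% and 1,434.7/1,915 = 74.9%. Gap 12.9 points, bias 1.3 mL/min, SE 0.89, false-positive rate 30%.
- Whole grid, 380/2,220: gap 3-13 points, bias 0.2-1.9 mL/min, false-positive rate 5-58%.
- Whole grid, change taking hold only after 1,300: gap 7-35 points, bias 0.4-5.2 mL/min, rate 6% to above 99%.

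Within a wave, if DTG use does not depend on genotype, the bias is zero. Adjusting for regimen or enrolment period therefore removes it in this model.

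**The case against.** **The list is open.** Section 8.0 introduces its covariates with a word that allows others, so ART terms are unspecified rather than excluded. That is fair, but Aim 2 names DTG explicitly, and an open list lets the choice be made after the data are seen.

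**The artefact may be small.** The equation includes cystatin C, which should dilute a creatinine artefact, and 0.2 mg/dL is an upper figure in one place. Both points stand and are reasons for the wide range of A. At the low end of the grid the false-positive rate stays near 5%.

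**Recruitment was widened, not replaced.** The second site is described as planned, and recent starters are prioritised to balance ART duration. This stands too.

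Some stronger readings are tempting but not supported:
- *A DTG gap of 20-40 points, enough by itself to create a significant result.* At the documented 380/2,220 split, 20 points exceeds even the ceiling of 19.5. Such gaps need the change to take hold much later, which is possible but undocumented.
- *Ethnicity and site terms would not help because DTG uptake drifts over time within site.* Genotype is fixed at birth. Under this mechanism it tracks enrolment date only through ethnicity and site mix, so within those groups the drift does not confound.
- *Aim 1 breaks the plan's own commitment to account for DTG.* That sentence concerns Aim 2 participants, and Section 8.0 meets it with the baseline covariate and the time-varying, mediation and interaction analyses. Aim 3 reuses the Aim 2 analyses.
- *The Aim 2 covariates and the 2% tenofovir toxicity rate in Table S7 are undermined.* Randomisation handles time on ART and tenofovir use in the arm comparison, and Table S7 is a power input. Neither bears on bias in Aim 1.

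**Conclusion.** The point holds as a gap in Aim 1 pre-specification. Recruitment mix and the DTG rollout overlap in time, the plan itself says DTG lowers calculated eGFR artificially, and no Aim 1 list names a covariate that would break the link. The bias would run towards the stated hypothesis.

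Its size cannot be fixed from the documents. The range of roughly 0.2-2 mL/min, for a change taking hold after 380 enrolees, rests on the assumed artefact, SD, carriage and DTG shares. Against a half-width of about 1.8 mL/min, this runs from negligible to enough to inflate false positives materially. If DTG uptake proves similar in the two genotype groups, little or no bias arises. The effect on CKD was not sized, because the plan does not give the share of ART-treated participants near the eGFR threshold.

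Separately, the Section 6.0 reassurance on tenofovir rests on a mean ART duration that Section 3.0 sets out to change, so the two passages need reconciling. This change should be made; it does not threaten the Aim 2 treatment comparison.

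**What to change.** 1. In Section 8.0, Specific Aim 1, pre-specify DTG use at the Aim 1 blood sample, time on ART, ethnicity, and site or enrolment period in the linear model for eGFR and in the modified Poisson models for reduced eGFR and CKD.
2. State that the adjusted model, not the crude Wilcoxon test, is the main eGFR result.
3. Reconcile the Aim 1 covariate lists in Sections 5.0 and 8.0 into one.
4. Reconcile the Section 6.0 statement on ART duration with the Section 3.0 recruitment change.

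The cost is SAP wording and a few degrees of freedom among 2,600 people. Ethnicity is already collected, and ART duration is needed for eligibility. ART regimen is not in the Section 5.0 list of Aim 1 data, and the Aim 2 covariate covers only the 280 randomised. The team must therefore confirm that regimen at sampling can be taken from the chart for every Aim 1 participant. No change to the Aim 2 covariates or Table S7 is needed for this point.

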enroll 280 eligible patients from Specific Aim 1 for 1:1 randomization in our RCT for Specific Aim 2. Based on our prior experience with ongoing RCTs in the study location, we anticipate that enrollment into Aim 2 will take 12 months and there will be 10% loss to follow up at end of year 2, yielding 252 patients on study (126 per arm). Aim 2A: At 2 years, we hypothesize that a higher proportion of intervention participants will regress from microalbuminuria to normoalbuminuria (uACR < 30 mg/g) with a hazard ratio (HR)= 2.50. Using the logrank test, we will have approximately 80% power if the rate of regression in the SOC arm is at least 12%, and 90% power if that rate is 16% or higher with a 1.7% type I error¹³⁶. (The type I error rate was set at 5%/3=1.7% to account for multiple testing and the fact that we have 3 primary endpoints.) See Tables 3 and 4. Aim 2B: At 2 years, we hypothesize that a higher proportion of patients in the SOC arm. namely 60% vs. 25% in the intervention arm (HR≈0.42), will progress from microalbuminuria to macroalbuminuria (uACR > 300 mg/g). With 126 patients per arm (after removing 10% loss to follow-up), we will have >95% power for Aim 2B with a 1.7% type I error. See Tables 5 and 6. Figure 3 shows changes in Aim 2A power for varying SOC regression rates and changes in Aim 2B power for varying sample size. The sample size for Aim 2C is such that we will have approximately 80% power to detect at the alpha=0.017 level a difference in the log-transformed mean uACR of 0.24, which is approximately 0.41 standard deviations. These power calculations are likely conservative, as they do not incorporate baseline covariates, which will be included in the actual analyses (see below) and should improve power; in addition, the uACR analysis will incorporate multiple longitudinal measures per person whereas these power calculations only assume a single final measurement per person.

The sample size was chosen to have sufficient power for all primary endpoints. Tables S1-S8, investigating power and detectable alternatives for the secondary endpoints with a total sample size of 280 are provided in Appendix B. In short, we anticipate low power to detect differences between intervention arms in the doubling of serum creatinine, all-

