cause mortality, and tenofovir toxicity because the expected rates for these events in the placebo arm are anticipated to be small (i.e., 2-20%, <10%, and 2%, respectively). We should have sufficient power to detect meaningful differences in eGFR, quality of life scores, and blood pressure.

alpha	Events Needed	Approx Rate SOC	Approx Rate Exp	Patients per Arm	Power
0.010	38	0.12	0.3	100	0.595
0.010	50	0.16	0.4	100	0.751
0.010	45	0.12	0.3	120	0.695
0.010	60	0.16	0.4	120	0.838
0.010	53	0.12	0.3	140	0.775
0.010	71	0.16	0.4	140	0.898
0.010	60	0.12	0.3	160	0.838
0.010	81	0.16	0.4	160	0.938
0.010	68	0.12	0.3	180	0.886
0.010	91	0.16	0.4	180	0.963
0.017	38	0.12	0.3	100	0.666
0.017	50	0.16	0.4	100	0.807
0.017	45	0.12	0.3	120	0.758
0.017	60	0.16	0.4	120	0.880
0.017	53	0.12	0.3	140	0.828
0.017	71	0.16	0.4	140	0.928
0.017	60	0.12	0.3	160	0.880
0.017	81	0.16	0.4	160	0.958
0.017	68	0.12	0.3	180	0.918
0.017	91	0.16	0.4	180	0.976
0.025	38	0.12	0.3	100	0.717
0.025	50	0.16	0.4	100	0.844
0.025	45	0.12	0.3	120	0.801
0.025	60	0.16	0.4	120	0.907
0.025	53	0.12	0.3	140	0.862
0.025	71	0.16	0.4	140	0.946
0.025	60	0.12	0.3	160	0.907
0.025	81	0.16	0.4	160	0.969
0.025	68	0.12	0.3	180	0.938
0.025	91	0.16	0.4	180	0.983
0.050	38	0.12	0.3	100	0.804
0.050	50	0.16	0.4	100	0.902
0.050	45	0.12	0.3	120	0.870
0.050	60	0.16	0.4	120	0.946
0.050	53	0.12	0.3	140	0.915
0.050	71	0.16	0.4	140	0.971
0.050	60	0.12	0.3	160	0.946
0.050	81	0.16	0.4	160	0.984
0.050	68	0.12	0.3	180	0.966
0.050	91	0.16	0.4	180	0.992

Table 3. Power calculation for regression

For these calculations, an HR of 2.5 was assumed.

Table 4. Detectable hazard ratios (HR) for regression

alpha	Events	Approx	Approx	Patients	Detectable
	Needed	Rate SOC	Rate Exp	per Arm	HR
0.010	42	0.12	0.35	100	2.88
0.010	52	0.16	0.41	100	2.59
0.010	48	0.12	0.32	120	2.69
0.010	59	0.16	0.39	120	2.43
0.010	54	0.12	0.31	140	2.54
0.010	67	0.16	0.37	140	2.31
0.010	59	0.12	0.29	160	2.43
0.010	74	0.16	0.35	160	2.21
0.010	65	0.12	0.28	180	2.34
0.010	81	0.16	0.34	180	2.13
0.017	41	0.12	0.33	100	2.76
0.017	50	0.16	0.40	100	2.49
0.017	46	0.12	0.31	120	2.58
0.017	58	0.16	0.37	120	2.34
0.017	52	0.12	0.29	140	2.45
0.017	65	0.16	0.36	140	2.23
0.017	58	0.12	0.28	160	2.34
0.017	72	0.16	0.34	160	2.14
0.017	63	0.12	0.27	180	2.25
0.017	79	0.16	0.33	180	2.06
0.025	40	0.12	0.32	100	2.66
0.025	49	0.16	0.39	100	2.41
0.025	45	0.12	0.30	120	2.50
0.025	57	0.16	0.36	120	2.27
0.025	51	0.12	0.28	140	2.37
0.025	64	0.16	0.35	140	2.16
0.025	57	0.12	0.27	160	2.27

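### Testing the three Aim 2 primary endpoints with Holm's step-down instead of a fixed 5%/3 each would add power at no cost in family-wise error; the present split is valid, so this is an optional improvement

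*Combined protocol and SAP*

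**What the plan says.** Section 1.2 lists three primary endpoints for Aim 2: regression to normoalbuminuria (Aim 2A in Section 8.0), progression to macroalbuminuria (2B) and mean change in uACR (2C). The only multiplicity rule is in the sample-size justification for Aim 2 in Section 8.0: "The type I error rate was set at 5%/3=1.7% to account for multiple testing and the fact that we have 3 primary endpoints". Power is then given at that level:

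- **2A:** the text says "we will have approximately 80% power if the rate of regression in the SOC arm is at least 12" per cent, and 90% if that rate is 16% or higher. The regression power table (Table 3 of Section 8.0, headed as a power calculation) has the rows "0.017 53 0.12 0.3 140 0.828" and "0.017 71 0.16 0.4 140 0.928" (alpha, events, control rate, experimental rate, patients per arm, power), with the note "For these calculations, an HR of 2.5 was assumed".
- **2B:** power above 95% for 60% versus 25% progression; Table 5 gives 0.984 at 140 per arm.
- **2C:** about 80% power to detect 0.24 on the log scale.

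The analysis text for Aim 2 says "We will test the hypotheses that regression and progression rates are different across arms using multivariable Cox regression models" and specifies a mixed model for uACR. It gives no significance level and no multiplicity procedure. No step-down, hierarchical or gatekeeping rule appears anywhere in the document.

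**The concern.** Under a fixed split, each endpoint must reach 5%/3 whatever the other two show. Aim 2B is planned at about 98% power, so it will usually be significant if the planned effect is real. A step-down procedure would then test the remaining endpoints at larger levels; the fixed split leaves that alpha unused. The power at stake is mainly for Aim 2A, which the text plans at about 80% in its less favourable scenario, and for the chance of significance on all three endpoints.

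**Working it through.** **Inputs.** 280 randomised 1:1, with 10% loss leaving 126 per arm (Section 8.0). 2A: HR 2.5, control rate 12% or 16% (Table 3). 2B: HR 0.42, 60% versus 25% (Table 5). 2C: difference 0.24 (Section 8.0), SD 0.58 (Appendix B, Table S1). Sidedness is not stated outright, but the hypotheses are worded as a difference and only two-sided levels reproduce the tables: one-sided 0.017 would give about 0.89 for 2A with 53 events. The correlation between the three tests is not given, so a common value of 0 to 0.6 is assumed.

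**Step 1: reproduce the plan's power.** Events = 126 x (sum of the two arm rates): 126 x 0.42 = 52.9, 126 x 0.56 = 70.6, 126 x 0.85 = 107.1, i.e. 53, 71 and 107. The mean test statistic is sqrt(events)/2 x |ln HR| for 2A and 2B, and difference/(SD x sqrt(2/126)) for 2C. Power = Phi(mean - 2.387) at two-sided 0.017.

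| Endpoint | Mean statistic | Recomputed | Plan |
|---|---|---|---|
| 2A, control 12% | sqrt(53)/2 x 0.916 = 3.34 | 0.829 | 0.828 |
| 2A, control 16% | sqrt(71)/2 x 0.916 = 3.86 | 0.930 | 0.928 |
| 2B | sqrt(107)/2 x 0.868 = 4.49 | 0.982 | 0.984 |
| 2C at 0.24 | 0.24/(0.58 x 0.126) = 3.28 | 0.815 | about 0.80 |

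The plan's figures hold.

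**Step 2: error control.** Holm compares the smallest p-value with 0.05/3, the next with 0.05/2 and the last with 0.05, stopping at the first failure. If k null hypotheses are true, the first of them to be rejected has been compared with at most 0.05/k, so the family-wise error is at most k x 0.05/k = 0.05 under any dependence. This matters because all three endpoints come from the same uACR series. Simulation with independent tests gave 0.049 with all three nulls true, 0.045 to 0.050 with two and 0.050 with one.

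**Step 3: bounds from the plan's own table.** Table 3 (140 per arm, control 12%) gives 2A power of 0.828 at 0.017, 0.862 at 0.025 and 0.915 at 0.05. Power under Holm must lie between the first and the last (apart from the rounding of 0.05/3).

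**Step 4: the effect for 2C.** The 0.24 is a detectable difference, so power near 80% follows by construction. Section 1.2 hypothesises a 40% fall against a 10% rise. Read as a ratio, that is ln(1.1/0.6) = 0.61 log units, with mean statistic 0.606/(0.58 x 0.126) = 8.3 and power above 0.999 at 0.05/3.

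**Step 5: Holm against Bonferroni at 0.05/3.** Trivariate normal simulation with the means above; ranges cover correlations 0 to 0.6.

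| Scenario (2B as planned) | Power for | Bonferroni | Holm |
|---|---|---|---|
| Control 12%, 2C at 0.24 | 2A | 0.83 | 0.90-0.91 |
| | 2C | 0.81 | 0.89-0.90 |
| | all three | 0.66-0.72 | 0.82-0.85 |
| Control 16%, 2C at 0.24 | 2A | 0.93 | 0.96-0.97 |
| Control 12%, 2C at 0.61 | 2A | 0.83 | 0.91 |
| | 2C | >0.99 | >0.99 |
| | all three | 0.81-0.82 | 0.91 |

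2B itself gains at most 1 point.

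**Step 6: dependence on the other effects (control 12%).** If 2B is null and 2C is at 0.24, 2A gains about 2 to 3 points. If 2B is null but 2C is at 0.61, 2C is rejected almost surely, 2A is tested at 0.025 or better, and the gain is about 4 points (Table 3: 0.862 at 0.025). If only 2A is real, it moves from 0.826 to 0.827. With all mean statistics at 70% of plan and correlation 0, it moves from 0.476 to 0.575.

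**The case against.** The strongest reply is that nothing here is wrong. Bonferroni is valid, the powers are right, each endpoint meets its target, and simultaneous intervals follow directly from the split. The plan also calls its power conservative, because baseline covariates and the repeated uACR measurements are left out of the calculation; higher true power leaves less for Holm to add. All of this stands.

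It also stands that the gain is easily overstated. A reader might infer that 2A and 2C are both planned at only about 80% power, and that the chance of winning on all three is therefore only about two in three. The documents do not support that for 2C, where 0.24 is a sensitivity figure. At the effect hypothesised in Section 1.2, 2C power stays at about 0.99 even if the SD were 1.0, and 0.96 if it were doubled to 1.16 (both SDs are assumptions). For 2A, the plan gives a 16% scenario as well as the 12% one.

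A further reply is that the 5%/3 stands in a sample-size paragraph, and sizing at that level is compatible with a Holm analysis. That is fair: the documents do not say that the final tests must use the fixed split. But they name no other procedure, and the analysis text is silent, so the fixed split is the only rule a reader can apply. None of these replies gives a reason to prefer the fixed split for testing, apart from the simpler intervals.

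**Conclusion.** A cheap improvement, not an error. Holm keeps the 5% family-wise error and never does worse than Bonferroni at 0.05/3. The firm gain is in Aim 2A, provided 2B has its planned effect: about 7 to 8 points at a 12% control regression rate and about 3 to 4 at 16%. The gain in 2C applies only if the true difference is near 0.24 log units. The chance of significance on all three (control 12%) rises by about 13 to 16 points with 2C at 0.24, and by about 9 to 10 with 2C at the hypothesised effect.

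These figures assume 126 per arm, two-sided tests, a common correlation of 0 to 0.6 and, for the 0.61, that the hypothesised percentage changes act as a ratio. The gain needs more than one real effect, and the chance of at least one significant endpoint is identical under both procedures. A reader should not infer that the trial is underpowered or that its type I error is materially wrong. The rounded 1.7% used three times sums to 5.1%, which exact 0.05/3 removes.

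**What to change.** Before unblinding, state in the Aim 2 sample-size justification and again in the Aim 2 analysis text of Section 8.0: *The three primary hypotheses will be tested two-sided with Holm's procedure at overall alpha 0.05 (ordered p-values compared with 0.05/3, 0.05/2 and 0.05).* Keep the existing power figures at 1.7% as a conservative floor.

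The cost is one sentence in two places, with no extra patients, visits or data. The one drawback is that simultaneous confidence intervals matching Holm are less simple; report 98.3% Bonferroni intervals alongside, noting that such an interval may include no effect when Holm rejects. If the team prefers to keep Bonferroni, the analysis text should still name it, at exact 0.05/3.
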